Viral load testing: For research purpose, blood will be drawn at three times from female participants (once during pregnancy and twice postpartum). This will be done by trained, experienced health care

providers with sterile equipment at the UTH laboratory. There is an extremely low risk of infection or any other physical repercussions from the procedure. Research-only blood draws may cause some physical discomfort to participants during the process. This procedure is routinely done for patients living with HIV.

Behavioral questionnaires: One potential risk to participants involved in this study is emotional discomfort, such as embarrassment or sadness when asked sensitive questions during the survey. These risks may occur, but we do not anticipate the risks resulting in any long-term psychological or physical distress or impairments. There are no physical, legal, or financial risks involved in the survey. The only potential risk is an emotional response to the sensitive questions being asked, including intimate partner violence experiences and issues related to living with HIV. Another potential risk could be social risk (e.g. risk to reputation) if information revealed during the course of the survey were to be disclosed outside of the research team (e.g., participants' HIV-positive status was revealed to family or the community).

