Data monitoring procedures: Recruitment goals will be carefully monitored by the Study Coordinator and the PI. We will also monitor the presence of any missing data and loss to follow-up to ensure the validity and integrity of the data. We will closely track incoming numbers of participants via ongoing recruitment activities, and weekly and monthly reports will be compiled by the study staff. We will utilize similar procedures to monitor any missing data or missed follow-up assessments. All study data (questionnaires and viral loads) will be coded with a participant study ID to maximize confidentiality. The codes that link the name of the participant and the study ID will be kept confidential in a secured database accessible only by the PI and limited research staff. All study data will be collected and managed using REDCap (Research Electronic Data Capture). REDCap is a secure web application designed to support data capture for research studies, providing user-friendly web-based case report forms, real-time data entry validation (e.g. for data types and range checks), audit trails and a de-identified data export mechanism to common statistical packages. The database is hosted at the University of Colorado–Denver Development and Informatics Service Center, which will be used as a central location for data processing and management. Laptops and handheld devices will be encrypted, password protected, and backed up daily. Tablets will be used to collect much of the data via the REDCap mobile application, which allows data to be entered and securely stored on the device, and later, upon internet connectivity, sent to the host server. The PI and Study Coordinator will provide ongoing monitoring of the study progress. All data will be kept confidential with exception of limits to confidentiality legally required to be reported to law enforcement in Zambia (child abuse).

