Data-related risk reporting and action plan: We will closely track incoming numbers of participants via ongoing recruitment activities, and weekly and monthly progress reports will be compiled by the study staff and reviewed by the Study Coordinator and the PI. We will utilize similar procedures to monitor any missing data. Recruitment and missing data reports will be monitored weekly by the Study Coordinator and monthly by the PI. All data will be protected on firewall-protected servers at the University of Colorado. Any identification of recruitment rates or follow-up rates that represent threats to our ability to sufficiently answer the research questions will be met with action by the PI to intervene to remedy the shortcomings, including adding additional recruitment sites (antenatal clinics). Should a situation arise of insufficient power or early detection of research questions, the PI will review and discuss with NIMH halting the study, when and if needed, and would report such action to all monitoring bodies. Completion rates of intervention activities will be monitored in parallel fashion using study logs.

Safety-related risks: Safety-related risks to participants could consist of: 1) emotional discomfort or distress resulting from sensitive questions being asked on the behavioral questionnaires pertaining to HIV and/or relationship issues; 2) social risk (e.g. risk to reputation) if confidential information revealed during the course of the study were to be disclosed outside of the research team; 3) tension, conflict or violence between the partners 4) risks related to biospecimen collection (research-only blood draws), such as physical discomfort, and the unlikely potential for infection or other physical repercussions from

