the procedure; and 5) risks associated with participation in the intervention activities (group education sessions and/or couples counseling visits). Pregnant and postpartum women and infants also face risks of adverse pregnancy outcomes (e.g., preterm birth, miscarriage) and infant/maternal mortality, which are common in the study community but are not likely to be related to study participation but will be monitored during the course of the study. There is one exception to confidentiality: this study does not anticipate any mandatory reporting information being revealed in the course of the study; however, if child abuse is disclosed, Zambian law requires a report to law enforcement. Detailed protocols will be in place regarding the possibility of tension, conflict or violence between partners during or outside the counseling sessions. Protocols will be in place to monitor and respond to any instances reported by the participants of any type of negative relationship or other social event, and proper action will be taken, including the provision of referral for services depending on the specific event and participant preferences.

Safety-monitoring procedures: All safety-related risks will be monitored routinely, including during recruitment and enrollment, intervention sessions, and data collection (questionnaires, medical record reviews, and biospecimens). All participants will complete an informed consent process emphasizing their rights and the voluntary nature of the study, which will be read aloud from an information sheet (due to low literacy levels in the target population) and followed by participant signature/thumbprint. The intervention has been carefully designed to minimize conflict within couples and ensure privacy, including protecting confidential information (e.g., HIV status) from one's partner and to monitor all confidential information to protect subject privacy and inadvertent social harms. During study procedures, at any sign of participant discomfort or distress, or by request, the activity will be halted and applicable support and referrals (e.g., mental health or domestic violence services) will be provided. Confidentiality will be assured to all participants at the time of consent; they will be assured their answers or responses cannot be used against them for any reason, or for denial of any medical treatment.

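### The promise that answers can never be used against participants, and the statement that the survey carries no legal risk, conflict with the plan's duty to report disclosed child abuse to law enforcement

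*Combined protocol and SAP*

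**What the plan says.** All the relevant text is in Section IV.D of the combined protocol and SAP.

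- **Behavioral questionnaires:** "There are no physical, legal, or financial risks involved in the survey". The next sentence begins: "The only potential risk is an emotional response to the sensitive questions being asked". The one after that adds a social risk, such as damage to reputation, if information leaves the research team.
- **Safety-related risks:** a five-item list covers distress from the questionnaires, social risk from disclosure, "tension, conflict or violence between the partners", blood-draw risks, and risks of the intervention activities. Legal risk is not an item. Later in the same paragraph, confidentiality is said to have a single exception: "if child abuse is disclosed, Zambian law requires a report to law enforcement". The sponsor adds that it does not expect such information to arise.
- **Data monitoring procedures:** the same exception is stated for all study data, which that paragraph defines to include the questionnaires.
- **Safety-monitoring procedures:** confidentiality is assured to everyone at consent, and "they will be assured their answers or responses cannot be used against them for any reason, or for denial of any medical treatment". No exception is attached.

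The description of the informed consent process, also in Section IV.D, says that risks and the handling of privacy will be explained. Section IV.E says that consent will describe every potential risk.

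**The concern.** The Safety-monitoring text prescribes something participants are to be told, and its wording is absolute. The plan elsewhere accepts a legal duty that makes it inaccurate. Staff who follow the text as written would give an assurance that the study cannot keep if a participant discloses child abuse.

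Consent is read aloud because literacy in the target population is low, so the spoken words are what participants have to rely on. Both partners are then interviewed face to face on sensitive family matters, including partner violence, at baseline and at 6 and 24 weeks postpartum. What is at stake is the accuracy of what people are told before they decide to take part and to answer.

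**Working it through.** No arithmetic applies; the check sets the statements side by side.

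**1. Assurance against reporting duty.** The assurance covers any reason and any answer. The reporting duty covers any child abuse disclosed in the course of the study, and nothing limits it to abuse by someone other than the respondent. Take a respondent whose own answer discloses abuse that he or she committed. The duty sends that answer to law enforcement, while the assurance says it cannot be used against that person. Both cannot be true. The conflict is direct in that case. It is weaker where the respondent reports someone else's conduct.

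**2. No legal risk against reporting duty.** The Data monitoring paragraph applies the exception to all study data, including questionnaires, so a survey answer can trigger a report. That is a legal risk of the survey, and the questionnaire paragraph denies that any exists.

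**3. Sole risk against the next sentence.** The questionnaire paragraph gives emotional response as the only risk and immediately adds a social risk. It is inconsistent on its own terms.

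**4. Does the general consent text repair this?** Not as written. The consent content list names risks and privacy but not the limit on privacy. Section IV.E promises that all potential risks will be described, but neither risk description in Section IV.D contains the legal one: one denies it and the other omits it. The two statements of the exception do not say that participants are told of it. The only specific assurance the protocol prescribes on how answers may be used is the unqualified one.

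**The case against.** The strongest reply is that the plan is open about the limit. It states the exception twice and commits to explaining privacy and all potential risks at consent. The consent pages were removed from the public document and may state the exception plainly; their absence is not a fault of the plan. The sponsor expects no reportable disclosure, and nothing shows that the survey asks about child abuse.

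Much of this stands, and it rules out several stronger readings.

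- **That participants do answer under a false assurance, or that the plan knowingly misleads them.** A reader might infer this, but it cannot be shown without the consent pages, and nothing in the text supports intent. Nor is there any sign that the no-risk sentence in the questionnaire paragraph is read to participants; it is protocol risk text.
- **That listing partner violence contradicts the denial of physical risk.** The denial is confined to the survey. The violence item belongs to a list for the whole study, which has a separate item for questionnaire distress, and the protocols for violence are described in relation to the counseling sessions. Partners are surveyed separately. Because IPV answers shape counseling that both partners attend, one might suspect that a partner could deduce a disclosure. That is an inference the protocol does not make. It is a tension, not a contradiction.
- **That trust, honest reporting or retention will suffer.** The documents give no basis for this.

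What does not stand is the suggestion that disclosure elsewhere cures the problem. If the consent form does state the exception, participants would still be given an assurance that contradicts it.

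**Conclusion.** The point holds for the legal limit only. The assurance under Safety-monitoring procedures and the denial of legal risk under Behavioral questionnaires are both broader than the reporting duty the protocol accepts, and the sole-risk wording is contradicted by the following sentence. The text should be corrected because it governs what participants are told.

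Its size is that of a wording error with an ethical consequence. The assurance is meant for every participant (238 couples × 2 = 476 people planned), but that counts those who would hear it, not those harmed. The number of reports cannot be estimated from the documents. No endpoint, sample size, power figure or analysis is affected.

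The conclusion rests on two assumptions: that the assurance would be given as worded, and that the reporting duty extends to a respondent's own disclosed conduct. The text indicates the first and does not exclude the second. It does not depend on what the consent pages say.

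**What to change.** Amend Section IV.D as follows:

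1. **Safety-monitoring procedures:** qualify the assurance with an exception for reports of child abuse that Zambian law requires.
2. **Behavioral questionnaires:** take the word legal out of the no-risk sentence, name the reporting duty there, and reword the sole-risk sentence so that it agrees with the social risk that follows.
3. **Safety-related risks:** add the legal consequence of a mandatory report to the list.
4. **Informed consent process:** state that participants are told of this limit at consent, before they answer the survey. Check the consent form and the script read aloud against the amended text.

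The cost is a few sentences in the protocol and, if the exception is not already there, in the consent script. No procedure or analysis changes. The downside is that a few participants may disclose less once they know the limit.

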Safety-related risk reporting and action plan: The PI will be responsible for executing the DSMP, conforming to rigorous standard monitoring procedures for participant safety, and complying with reporting requirements. The PI has primary responsibility for the overall conduct of the study, including the safety of human subjects. The PI will ensure appropriate (1) conduct of the informed consent process (e.g. that informed consent is obtained before proceeding with study procedures); (2) enrollment of study subjects; (3) collection and analysis of data; (4) implementation of study procedures to ensure consistent monitoring of subjects for possible adverse events; (5) immediate receipt and review of standardized and detailed adverse reports and reporting of to the Institutional Review Boards; and (6) maintenance of the privacy and confidentiality of study subjects. The PI will be in contact with the local Zambian research team (calls biweekly) throughout the study to review progress and address any human subject safety concerns. The PI will also review all electronic study data monthly from REDCap to ensure that the DSMP and all protection of human subject protocols are followed. The PI will conduct in-person reviews of the study procedures and data collection biannually in Lusaka. If any increased risks are identified during the study, the PI will review and determine the adequacy of human subject protections, making recommendations for enhancing these protections if deemed necessary.

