Aim 1: Compare service utilization and PMTCT outcome indicators in two study conditions	Primary outcome: female viral suppression at 24 weeks postpartum (<1000 RNA copies/ml)	Intermediate outcomes: 
 ➤ female viral suppression at 6 weeks postpartum ➤ female self-reported ART adherence (visual analog scale using 3-day, one-week, and one-month recall periods) ➤ facility birth ➤ exclusive breastfeeding to six months ➤ uptake of pediatric HIV testing (and treatment if positive) ➤ postpartum family planning 	Research-only blood draws (female partner), + Behavioral surveys	Independent t-tests and Pearson's chi-square tests; logistic regression models with generalized estimating equation; survival analysis with cumulative incidence across time, Kaplan-Meier curves, mixed-effects Cox proportional hazards models
Aim 2: Establish the effect of the	Intrapersonal mechanisms: 
 ➤ mental health 	Interpersonal mechanisms: 
 ➤ IPV past month ➤ Intimacy and trust 	Behavioral surveys	Mediation analysis with structural equation modeling

intervention on intra- and inter-personal mechanisms influencing PMTCT outcomes	
 ➤ self-esteem ➤ perceived stigma ➤ perceived partner acceptance 	
 ➤ Communication skills ➤ problem-solving skills ➤ joint decision-making ➤ Conflict resolution skills ➤ Relationship satisfaction ➤ Perceived social support ➤ Communal coping 		(SEM)
--	---	---	--	-------

2. Sample size calculation: Based on the primary outcome (viral load) and a projected 25% loss to follow-up (10% due to break-ups and 15% due to other causes), we require 238 total couples (119 couples per arm) to achieve the sample size target of 178. This target is based on a Pearson's chi-squared two-sample proportions test with a power of 0.80 and alpha of 0.05, assuming a delta of 0.20 at the 6-month follow-up between the intervention and control arms. Based on recent studies from the region,⁵⁸⁻⁶⁰ we estimate viral suppression at 6-months to be 55% in the control arm and 75% in the intervention arm. For the intermediate and mediating variables on the behavioral survey, the proposed sample size will enable us to detect a hazard ratio of 0.75, power of 0.80, and alpha of 0.05, using a two-sample comparison of survivor functions exponential test.

G. Summarize Knowledge to be Gained:

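### The protocol lets early detection of an answer prompt a halt, while the analysis plan has one fixed test at 0.05 and no rule for early stopping

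*Combined protocol and SAP*

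**What the plan says.** Four places bear on this.

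- **Section IV.D, data-related risk reporting and action plan.** The halting provision reads: "Should a situation arise of insufficient power or early detection of research questions, the PI will review and discuss with NIMH halting the study". It adds that any such action would be reported to the monitoring bodies. No threshold, timing or number of looks is attached. The sentence before it deals separately with poor recruitment or follow-up, and its remedy is action by the PI such as adding clinics.
- **Section IV.D, data monitoring procedures.** "All study data (questionnaires and viral loads) will be coded with a participant study ID", and the same paragraph places all study data in REDCap. Viral load supplies the primary endpoint.
- **Section IV.D, safety-related risk reporting and action plan.** "The PI will also review all electronic study data monthly from REDCap". The sentence goes on to give the purpose, which is to check that the monitoring plan and the human-subject protections are being followed.
- **Section IV.F, statistical analysis and sample size.** The design rests on a "chi-squared two-sample proportions test with a power of 0.80 and alpha of 0.05". No interim analysis, boundary, alpha spending, futility rule or adjusted estimate is described.

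Section IV.C has the PI helping to supervise delivery of the intervention. The documents describe neither masking of the PI nor an independent data monitoring committee.

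**The concern.** The natural reading of the early-detection ground is that the research question appears to be answered before the planned end. That judgement needs outcomes by arm. It is unlikely to mean slow accrual or poor retention, because the preceding sentence already covers those. The protocol therefore names an outcome-related reason for stopping, while the analysis plan is valid only if the result plays no part in deciding when to stop.

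Two things are at stake. A stop prompted by a favourable early difference adds chances of a false positive beyond the nominal 5%. It also selects for estimates that happen to be high at that moment. The second matters particularly here, because Section IV.G says that the study is to supply the data for a larger trial. An exaggerated effect would lead to that trial being planned too small.

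**Working it through.** **Step 1: reproduce the planned sample size.** Inputs from Section IV.F.2: "we estimate viral suppression at 6-months to be 55% in the control arm and 75% in the intervention arm"; alpha 0.05; power 0.80; "a projected 25% loss to follow-up (10% due to break-ups and 15% due to other causes"). Sidedness is not stated and is taken as two-sided.

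n per arm = [1.96·√(2·0.65·0.35) + 0.842·√(0.55·0.45 + 0.75·0.25)]² / 0.20²
= [1.322 + 0.555]² / 0.04 ≈ 88.1, rounded up to 89.

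- Evaluable: 2 × 89 = 178, as stated; power at 89 per arm is 80.4%.
- Enrolled: 178 / (1 − 0.25) = 237.3, rounded up to 238 (119 per arm), as stated.
- A one-sided test would need 70 per arm and a continuity-corrected test 98, and neither matches.

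The planned figure is thus reproduced as one two-sided test, done once, with no allowance for looking early.

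**Step 2: what stopping on an unadjusted difference would do.** The documents give no number of looks. As an assumption, take K equally spaced looks, with stopping at the first two-sided p<0.05. With Zₖ = (X₁ + … + Xₖ)/√k and independent standard normal X under the null, the type I error is the probability that any |Zₖ| exceeds 1.96. This was simulated with 400,000 null trials. A binary version used 100,000 trials per scenario, with 89 per arm at the last look and 55% suppression in the control arm.

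| Looks | Type I error, normal theory | Type I error, binary (55% in both arms) | Mean reported difference, true 0.20 | Mean if stopped early, true 0.20 | Mean if stopped early, true 0.10 |
|---|---|---|---|---|---|
| 1 | 5.0% | 5.0% | 0.200 | – | – |
| 2 | 8.3% | 8.3% | 0.220 | 0.276 | 0.250 |
| 3 | 10.7% | 11.0% | 0.233 | 0.280 | 0.255 |

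**Step 3: why the estimate is exaggerated.** At a halfway look with 44 per arm, the smallest difference that reaches p<0.05 is about 1.96·√(2·0.65·0.35/44) = 1.96 × 0.102 ≈ 0.20. Any trial stopped there for benefit reports roughly 0.20 or more, whatever the true effect.

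**Step 4: separate the two grounds.** Section IV.D describes the data-related risk as collecting too little data to answer the aims. In that context, insufficient power most naturally means a shortfall in recruitment or follow-up. A halt based on pooled rates does not use the difference between arms, so it leaves the type I error alone and costs power and precision. Only the early-detection ground, or a power judgement based on observed effects, creates the problem in Step 2.

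**The case against.** The strongest reply is that nothing in the documents schedules an efficacy look. The monthly review of all data sits in the safety section and has a protective purpose. The monthly reports named alongside the halting provision cover recruitment and missing data. Nothing links the safety review to halting, and access to viral loads is not the same as testing them. All of this stands. A reader might infer that the PI tests efficacy every month and that the true error rate is therefore well above 10%. The documents do not support that, and the figures above are conditional on an assumed number of looks and automatic stopping.

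A reader might also infer that the PI can stop the study alone, or that the insufficient-power ground inflates alpha too. Neither holds: a halt is discussed with NIMH and reported, and the power ground reads as a feasibility provision.

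Timing limits the practical threat. First group sessions are planned over three months, and the primary endpoint falls 24 weeks, about 5.5 months, after delivery. On that schedule entry closes before any primary result exists, although the COVID-19 limit on group size could lengthen entry. An early stop would mainly cut follow-up short. It could still bias the result, because deliveries, and so 24-week results, are spread over time.

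What the reply does not remove is the stated ground itself. Consulting NIMH does not control the error rate when neither party has a prespecified criterion.

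**Conclusion.** The point holds in a limited form. The protocol names a reason for halting that its analysis plan cannot accommodate, and the person who would raise it can see the accumulating endpoint and is not described as masked. The 5% error rate and the final estimate are therefore unprotected. It would be wrong to say that they are already inflated by a known amount.

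If the ground were used with unadjusted tests, the type I error would be about 8% with two equally spaced looks and 11% with three. Trials stopped early would report about 0.28 when the true difference is 0.20, and about 0.25 when it is 0.10. These figures assume a two-sided test, equal spacing and stopping at the first p<0.05, none of which the documents specify. The conclusion also rests on reading early detection as an answer visible in the outcome data. The phrase is unclear, and that is a further reason to remove it.

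**What to change.** - In Section IV.D, delete early detection as a ground for halting.
- In Section IV.F, state that there is no interim efficacy analysis and that postpartum viral loads will not be tabulated or tested by arm before database lock.
- Keep insufficient power as a ground, but define it by recruitment and follow-up rates pooled over arms, not by observed effects. Deleting it would remove a legitimate provision for failed accrual or retention.
- Leave safety monitoring and safety halting as they are, including any review by arm. Only the intervention arm receives the counselling visits and no independent committee is described, so pooling safety data could hide harm specific to that arm.

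The cost is a few sentences and a restriction on tabulating viral loads by arm. Alpha stays 0.05 and the sample size stays 178 evaluable and 238 enrolled. The sponsor gives up only an undefined option to stop early for efficacy. If that option is wanted, it needs a prespecified boundary. For example, an O'Brien-Fleming design with one look at half the evaluable couples uses nominal p of about 0.005 and then 0.048. In simulation with 178 evaluable it gave a type I error of 4.6% and power of about 80%.
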